5.2.1 Graded Laboratory Values

The criteria specified in the study protocol will be used to grade laboratory results as normal (no grade), mild (Grade 1), moderate (Grade 2), severe (Grade 3) or potentially life threatening (Grade 4). See Appendix 4 of the protocol for detailed DAIDS grading criteria on the relevant laboratory tests. For laboratory tests with criteria for both increased and decreased levels, analyses for each direction (ie, increased, decreased) will be presented separately.

Some lab tests require fasting to be graded (i.e. triglycerides and cholesterol). For those lab tests, Baseline will be defined as the last non-missing fasted evaluation prior to the first dose on Day 1.

5.2.1.1 Treatment-Emergent Laboratory Abnormalities

Treatment-emergent laboratory abnormalities will be defined as values that increase at least 1 toxicity grade from Baseline at any post-Baseline time point. If the relevant Baseline laboratory value is missing, any abnormality of at least Grade 1 observed within the time frame specified above will be considered treatment emergent.

5.2.1.2 Summaries of Laboratory Abnormalities

Treatment-emergent graded laboratory abnormalities will be summarized (number and percentage of subjects) by cohort, lab test, and treatment group; subjects will be categorized according to the most severe post-baseline abnormality grade for a given lab test.

For all summaries of laboratory abnormalities, the denominator is the number of subjects with nonmissing post-Baseline values.

The maximum post-Baseline grade observed will be tabulated for each laboratory test, and percentages will be based on the number of subjects with a post-Baseline evaluation of the specific laboratory test. A by-subject listing of graded laboratory abnormalities will be provided by cohort, subject number, and visit in chronological order. This listing will include all test results that were collected throughout the study for the lab test of interest, with all applicable severity grades displayed.

5.2.2 Ungraded Laboratory Values

Treatment-emergent abnormal direct bilirubin will be summarized by cohort and treatment group. A treatment-emergent abnormal direct bilirubin record is defined as a record with value > baseline and \geq ULN. The highest direct bilirubin measurement will be counted for each subject. A by-subject listing of visits with abnormal direct bilirubin will be provided.

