9.7 Laboratory Abnormalities and Other Abnormal Assessments as AEs or SAEs

Laboratory abnormalities (defined as outside of reference range) are usually not recorded as AEs or SAEs, unless they are clinically significant (see definition of AEs in [Section 9.1](#)), as determined by the Investigator. Clinical laboratory abnormalities that require medical or surgical intervention or lead to study drug interruption or discontinuation must be recorded as an AE or SAE, if applicable. The modified DAIDS Table for Grading the Severity of Adult and Pediatric AEs ([Appendix 4](#)) will be used to assess the severity of laboratory abnormalities. In addition, laboratory or other abnormal assessments (eg, ECG and vital signs) that are associated with signs and/or symptoms must be recorded as an AE or SAE if they meet the definition of an AE or SAE described in [Sections 9.1](#) and [9.6](#). If the laboratory abnormality or abnormal assessment is part of a syndrome or diagnosis, record the syndrome or diagnosis (eg, anemia), not the laboratory result (ie, decreased hemoglobin).

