Bilirubin Direct Bilirubin ¹³ , High > 28 days of age	NA	NA	> ULN with other signs and symptoms of hepatotoxicity	> ULN with life-threatening consequences (e.g., signs and symptoms of liver failure)
Total Bilirubin, High > 28 days of age	1.1 to < 1.6 x ULN	1.6 to < 2.6 x ULN	2.6 to < 5.0 x ULN	\geq 5.0 x ULN
Calcium, High (mg/dL; mmol/L) \geq 7 days of age	10.6 to < 11.5 2.65 to < 2.88	11.5 to < 12.5 2.88 to < 3.13	12.5 to < 13.5 3.13 to < 3.38	\geq 13.5 \geq 3.38
Calcium (Ionized), High (mg/dL; mmol/L)	> ULN to < 6.0 > ULN to < 1.5	6.0 to < 6.4 1.5 to < 1.6	6.4 to < 7.2 1.6 to < 1.8	\geq 7.2 \geq 1.8

Parameter	Grade 1 Mild	Grade 2 Moderate	Grade 3 Severe	Grade 4 Potentially life-threatening
Calcium, Low (mg/dL; mmol/L) ≥ 7 days of age	7.8 to < 8.4 1.95 to < 2.10	7.0 to < 7.8 1.75 to < 1.95	6.1 to < 7.0 1.53 to < 1.75	< 6.1 < 1.53
Calcium (Ionized), Low (mg/dL; mmol/L)	< LLN to 4.0 < LLN to 1.0	3.6 to < 4.0 0.9 to < 1.0	3.2 to < 3.6 0.8 to < 0.9	< 3.2 < 0.8
Cardiac Troponin I, High	NA	NA	NA	Levels consistent with myocardial infarction or unstable angina as defined by the local laboratory
Creatine Kinase, High	3 to < 6 x ULN	6 to < 10x ULN	10 to < 20 x ULN	≥ 20 x ULN
Creatinine, High **Report only one	1.1 to 1.3 x ULN	> 1.3 to 1.8 x ULN OR Increase to 1.3 to < 1.5 x participant's baseline	> 1.8 to < 3.5 x ULN OR Increase to 1.5 to < 2.0 x participant's baseline	≥ 3.5 x ULN OR Increase of ≥ 2.0 x participant's baseline
Creatinine Clearance ¹⁴ or eGFR, Low ¹⁴**Report only one	NA	< 90 to 60 ml/min or ml/min/1.73 m ² OR 10 to < 30% decrease from participant's baseline	< 60 to 30 ml/min or ml/min/1.73 m ² OR 30 to < 50% decrease from participant's baseline	< 30 ml/min or ml/min/1.73 m ² OR ≥ 50% decrease from participant's baseline or dialysis needed
Glucose (mg/dL; mmol/L) Fasting, High Nonfasting, High	110 to 125 6.11 to < 6.95 116 to 160 6.44 to < 8.89	> 125 to 250 6.95 to < 13.89 > 160 to 250 8.89 to < 13.89	> 250 to 500 13.89 to < 27.75 > 250 to 500 13.89 to < 27.75	≥ 500 ≥ 27.75 ≥ 500 ≥ 27.75
Glucose, Low (mg/dL; mmol/L) ≥ 1 month of age	55 to 64 3.05 to < 3.55	40 to < 55 2.22 to < 3.05	30 to < 40 1.67 to < 2.22	< 30 < 1.67
Lactate, High	ULN to < 2.0 x ULN without acidosis	≥ 2.0 x ULN without acidosis	Increased lactate with pH < 7.3 without life-threatening consequences	Increased lactate with pH < 7.3 with life-threatening consequences
Lipase, High	1.1 to < 1.5 x ULN	1.5 to < 3.0 x ULN	3.0 to < 5.0 x ULN	≥ 5.0 x ULN

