3 GENERAL CONSIDERATIONS FOR DATA ANALYSES

Analysis results will be presented using descriptive statistics. For categorical variables, the number and percentage of subjects in each category will be presented; for continuous variables, the number of subjects (n), mean, standard deviation (SD) or standard error (SE), median, first quartile (Q1), third quartile (Q3), minimum, and maximum will be presented.

Summary tables will be presented by cohort and treatment. For cohort A7, summary tables will be presented fasting order (i.e. “fed,fasted” or “fasted,fed”).

No formal inference is planned in this study. Hence, no multiplicity adjustment is required.

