5.2 Laboratory Evaluations

Laboratory data collected during the study will be analyzed and summarized using both quantitative and qualitative methods based on the Safety Analysis Set. The lab values that are below LLOQ or above the upper LOQ will be listed as such, and the closest imputed value will be used for the purpose of calculating summary statistics as specified in [Section 3.3](#).

A by-subject listing for laboratory test results will be provided by cohort, subject number, and visit in chronological order for hematology, serum chemistry, coagulation and urinalysis separately. Values falling outside of the relevant reference range and/or having a United States National Institutes of Health Division of AIDS (DAIDS) severity grade of 1 or higher will be flagged in the data listings, as appropriate.

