5.2.3 Summaries of Numeric Laboratory Results

Descriptive statistics will be provided by treatment and cohort for each laboratory test specified in the study protocol as follows:

- Baseline values
- Values at each post-Baseline visit
- Change from Baseline at each post-Baseline visit

A Baseline laboratory value will be defined as the last measurement obtained on or prior to the date/time of first dose of study drug. Change from Baseline to a post-Baseline visit will be calculated for any post-Baseline visit including follow-up visits. For Cohort A7 Period 2, Period 2 Baseline and Change from Period 2 Baseline will be used instead.

In the case of multiple values in a visit day, data will be selected for analysis as described in [Section 3.5.6](#).

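### SAP 5.2.2 counts a direct bilirubin exactly at ULN as a treatment-emergent abnormality; if ULN is the highest in-range value, that conflicts with protocol 9.7 and the SAP 5.2 listing flag (minor)

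*Combined protocol and SAP*

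**What the plan says.** SAP 5.2.2 covers direct bilirubin apart from the graded tests. Its rule is: "A treatment-emergent abnormal direct bilirubin record is defined as a record with value > baseline and \geq ULN". Each subject's highest measurement is counted, and the table is by cohort and treatment group. A by-subject listing of visits with abnormal direct bilirubin is also planned, but no rule for that listing is given.

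Four other places bear on the limit:

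- Protocol 9.7: "Laboratory abnormalities (defined as outside of reference range) are usually not recorded as AEs or SAEs".
- Protocol Appendix 4, direct bilirubin. Grades 1 and 2 are not applicable. Grade 3 is "> ULN with other signs and symptoms of hepatotoxicity" and Grade 4 is "> ULN with life-threatening consequences (e.g., signs and symptoms of liver failure".
- SAP 5.2, on which results are flagged in the laboratory listing: "Values falling outside of the relevant reference range and/or having a United States National Institutes of Health" (the sentence continues with a Division of AIDS grade of at least 1).
- SAP 5.2.1.1, for the graded tests: "Treatment-emergent laboratory abnormalities will be defined as values that increase at least 1 toxicity grade from Baseline".

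No section explains why the 5.2.2 limit includes ULN itself.

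**The concern.** The SAP uses two limits for the same analyte. On the usual reading of a reference range, a result equal to ULN is normal. SAP 5.2.2 would nevertheless tabulate it as a treatment-emergent abnormality if it exceeded Baseline. The 5.2 listing would show the same record without a flag, and protocol 9.7 would not call it abnormal.

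What is at stake is how one hepatic safety table reads in a first-in-human study with 6 active and 2 placebo subjects per cohort. Some subjects in that table could have had no out-of-range result, and a reader checking it against the listing would find no flag for them.

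**Working it through.** **Where the rules differ.** The documents give no figure to reproduce, so the first check is logical. Values are in units of ULN, with ULN taken as the highest in-range value.

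| Baseline → highest post-dose value | SAP 5.2.2 (at or above ULN) | Strict (above ULN) | Out of range, flagged in SAP 5.2 listing |
|---|---|---|---|
| 0.5 → 0.9 | no | no | no |
| 0.5 → 1.0 | **yes** | no | no |
| 1.0 → 1.0 | no | no | no |
| 0.5 → 1.1 | yes | yes | yes |
| 1.1 → 1.0 | no | no | no |
| 1.1 → 1.2 | yes | yes | yes |

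The inclusive and strict rules part only when Baseline is below ULN and the highest later value equals ULN. Such a value gets no grade flag either, because direct bilirubin has no Grade 1 or 2 in Appendix 4.

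**Effect of one subject.** Allocation is 6:2 (protocol 4.1.1 and 4.1.2). One subject is 1/6 = 16.7 points on active or 1/2 = 50 points on placebo.

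**Chance of at least one in an active group of 6.** If each subject has probability p of being such a case, the chance is 1 − (1 − p)^6. For assumed p of 1%, 5% and 10% this gives 5.9%, 26.5% and 46.9%.

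**Plausible frequency.** The documents give neither the laboratory's ULN nor its reporting step. SAP 3.3 analyses results entered as below 0.1 mg/dL as 0.05 mg/dL. That fits a 0.1 mg/dL step but does not prove one. A simulation with no drug effect therefore used stated assumptions:

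- 400,000 subjects per scenario and log-normal direct bilirubin.
- Log SD 0.4, 0.5 and 0.6 at within-subject correlation 0.5, plus correlations 0.3 and 0.7 at log SD 0.5.
- Assumed ULN of 0.2, 0.3 and 0.4 mg/dL, with values rounded to the step. In the 0.1-step runs, values below the lower limit were set to 0.05 mg/dL.
- One Baseline plus the post-dose chemistry samples in the protocol schedules: 4 in Part A (Days 2, 3, 5, 7) and 6 in Part B (Days 2, 4, 6, 8, and 3 and 7 days after the last dose).
- Three ways of placing ULN: (A) 2.5% of reported values exceed it; (B) it is the unrounded 97.5th percentile; (C) 2.5% of reported values are at or above it.

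The excess is the share of subjects counted by the inclusive rule but not by the strict one, in points. The central case is ULN 0.3 mg/dL, log SD 0.5 and correlation 0.5; ranges over all scenarios are in brackets.

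| Step | ULN placement | Part A | Part B |
|---|---|---|---|
| 0.1 mg/dL | A | 14.4 (7.9–28.9) | 17.8 (9.7–34.3) |
| 0.1 mg/dL | B | 10.0 (5.8–19.3) | 12.8 (7.2–24.7) |
| 0.1 mg/dL | C | 5.5 (3.8–7.5) | 7.4 (4.8–10.4) |
| 0.01 mg/dL | all | 1.0–1.1 (0.6–2.1) | 1.2–1.3 (0.7–2.6) |

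Cohorts A1–A5 plan 5 × 8 = 40 subjects and B1–B2 plan 2 × 8 = 16, so 56 in all. Extra subjects = 40 × Part A excess + 16 × Part B excess:

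- 0.1 step, A: 40 × 0.144 + 16 × 0.178 = 5.76 + 2.85 = 8.6
- 0.1 step, B: 40 × 0.100 + 16 × 0.128 = 4.00 + 2.05 = 6.0
- 0.1 step, C: 40 × 0.055 + 16 × 0.074 = 2.20 + 1.18 = 3.4
- 0.01 step: 0.40 to 0.44 plus 0.19 to 0.21, about 0.6

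**The case against.** **The conflict depends on how the laboratory states its range.** If normal means strictly below ULN, then at or above ULN is the same as out of range, and 5.2.2 agrees with protocol 9.7 and SAP 5.2. This stands as a condition on the point. The strict limit in Appendix 4 does not depend on that convention.

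**Appendix 4 is weak support.** Its two direct bilirubin cells also need signs of hepatotoxicity or life-threatening consequences, so they do not define an isolated abnormality. This is right: they show which side of ULN that analyte's own row uses, and no more. Grade 1 lactate in the same table starts at ULN, but lactate is not among the study's tests (protocol Table 2).

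**Protocol 9.7 governs AE recording, not tabulation.** That is its purpose, but it also says what a laboratory abnormality is, and the SAP 5.2 flag uses the same idea.

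**The displays differ by design.** A value above ULN but not above Baseline is flagged in the 5.2 listing and is not treatment-emergent in 5.2.2. This is true and intended. The fix removes only the discordance at exactly ULN.

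**An inclusive limit is a more sensitive hepatic screen.** That could be a defensible choice, but the SAP does not say it was made. The values remain visible elsewhere: SAP 5.2.3 summarises "Change from Baseline at each post-Baseline visit", and the by-subject listing shows every result.

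**The simulated sizes rest on assumptions.** They do, and they run from 0.6 to 34.3 points. They show that the reporting step decides whether ties at ULN are rare or common. They do not estimate what this study will see.

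**Conclusion.** The point holds as a minor inconsistency. If ULN is the highest in-range value, SAP 5.2.2 can report an in-range direct bilirubin as a treatment-emergent abnormality that the 5.2 listing leaves unflagged. The effect is limited to one descriptive table. Under the assumed inputs and no drug effect, it amounts to about 0.6 extra subjects of 56 with a 0.01 mg/dL step, or 3.4 to 8.6 in the central case with a 0.1 mg/dL step.

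Three stronger readings are tempting, and the documents do not support them.

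- **That the 5.2.2 listing also shows at-ULN values as abnormal.** It may, but its rule is not stated, and the inclusive limit is attached only to treatment-emergent records.
- **That the extra counts are pure noise, equal on drug and placebo.** Equal expected rates hold only if the drug does not move direct bilirubin. If it raises it, the inclusive limit also picks up additional rises on active treatment.
- **That the primary endpoint, dose escalation or stopping is affected.** Abnormal laboratory results are part of the primary endpoint (protocol 3.2.1), but no section says this table feeds it, and SAP 5.2.1.1 defines treatment-emergent laboratory abnormalities by grade. No cohort stopping criterion (protocol 7.2) or Data Review Committee trigger (protocol 10.6.2) uses the table. SAP section 3 adds: "No formal inference is planned in this study".

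**What to change.** In SAP 5.2.2, define the record as `value > Baseline and > ULN`, and state that the abnormal direct bilirubin listing uses the same `> ULN` limit.

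The cost is one operator in the text and the program, plus a clause for the listing. No new data, visits or tables are needed. The downside is that a rise stopping exactly at ULN drops out of this table. It remains in the change-from-Baseline summaries (SAP 5.2.3) and the by-subject laboratory listing (SAP 5.2).

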5.2.3 Summaries of Numeric Laboratory Results

Descriptive statistics will be provided by treatment and cohort for each laboratory test specified in the study protocol as follows:

- Baseline values
- Values at each post-Baseline visit
- Change from Baseline at each post-Baseline visit

A Baseline laboratory value will be defined as the last measurement obtained on or prior to the date/time of first dose of study drug. Change from Baseline to a post-Baseline visit will be calculated for any post-Baseline visit including follow-up visits. For Cohort A7 Period 2, Period 2 Baseline and Change from Period 2 Baseline will be used instead.

In the case of multiple values in a visit day, data will be selected for analysis as described in [Section 3.5.6](#).

5.2.4 Summaries of Categorical Laboratory Results

For categorical urinalysis parameters, the number and percentage of subjects in each category will be presented by treatment and cohort at each visit.

5.3 Body Weight and Vital Signs

Descriptive statistics will be provided by treatment and cohort for body weight, BMI, and vital signs (systolic and diastolic blood pressure [mmHg], pulse [beats/min], respiration [breaths/min], and body temperature [°C]) as follows:

- Baseline value
- Values at each post-Baseline visit
- Change from baseline at each post-Baseline visit

A Baseline value will be defined as the last available value collected on or prior to the date/time of first dose of study drug. Change from Baseline to a post-Baseline visit will be calculated for any post-Baseline visit including follow-up visits.

For Cohort A7 Period 2, Period 2 Baseline and Change from Period 2 Baseline will be used instead.

In the case of multiple values in an analysis window, data will be selected for analysis as described in [Section 3.5.6](#).

A by-subject listing of vital signs will be provided by cohort, subject number, and visit in chronological order. In the same manner, a by-subject listing of body weight, height, and BMI will be provided separately.

5.4 Prior and Concomitant Medications

Medications collected at Screening and during the study will be coded using the current version of the World Health Organization (WHO) Drug dictionary (WHO Drug Global 1SEP2022).

5.4.1 Prior Medications

Prior medications will be defined as any medications taken before a subject took the first study drug. Prior medications will be summarized by Anatomical Therapeutic Chemical (ATC) drug class Level 2 and preferred name using the number and percentage of subjects for each treatment and cohort. A subject reporting the same medication more than once will be counted only once within each ATC drug class. The summary will be ordered alphabetically by ATC medical class

and then by preferred term in order of descending overall frequency within each ATC medical class. For drugs with the same frequency, sorting will be done alphabetically.

A medication will be considered as a prior medication if it meets one of the following criteria:

- A medication with a start date prior to the first dose date of study drug will be included in the prior medication summary regardless of when the stop date is.
- If a partial start date is entered, the medication will be considered prior unless the month and year (if day is missing) or year (if day and month are missing) of the start date are after the first dose date.
- A medication with a completely missing start date will be included in the prior medication summary, unless otherwise specified.

Summaries will be based on the Safety Analysis Set.

5.4.2 Concomitant Medications

Concomitant medications will be defined as any prescription or over-the-counter preparation, including vitamins, medications, vaccinations, herbal preparations, and supplements (including traditional Chinese medicine) taken by a subject during the study. Use of concomitant medications will be summarized by ATC drug class Level 2 and preferred name using the number and percentage of subjects for each treatment and cohort. A subject reporting the same medication more than once within each ATC drug class will be counted only once when calculating the number and percentage of subjects who received that medication. Medications may appear under multiple ATC drug classes. The summary will be ordered alphabetically by ATC medical class and then by preferred term in descending overall frequency within each ATC medical class. For drugs with the same frequency, sorting will be done alphabetically.

A medication will be considered as a concomitant medication if it meets one of the following criteria:

- A medication with a start date prior to or on the first dose date of study drug, and continued to be taken after the first dose date.
- A medication started after the first dose date but prior to or on the last dose date of study drug.
- If a partial start date is entered, any medication with the month and year (if day is missing) or year (if day and month are missing) before the study drug stop date, and with the stop date after the first dose date of study drug. If a partial stop date is entered, any medication with the month and year (if day is missing) or year (if day and month are missing) after the first dose date of study drug.

- A medication started and stopped on the same day as the first dose date or the last dose date of study drug.
- Medications with completely missing start and stop dates, unless otherwise specified.

A medication with a stop date prior to the date of first dose date of study drug or a start date after the last dose date of study drug will be excluded from the summary.

Summaries of prior and concomitant medications will be based on the Safety Analysis Set.

All the prior and concomitant medications will be provided in a by-subject listing sorted by cohort, subject number, and administration date in chronological order.

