4.3.1 Duration of Exposure to Study Drug

Total duration of exposure to study drug will be summarized. Total duration of exposure will be defined as the last dose date of study drug minus the first dose date plus 1. If the last study drug dose date is missing, the latest date among the study drug end date, clinical visit date, laboratory sample collection date, and vital signs assessment date that occurred during the On-Treatment Period will be used for subjects included in the final analyses or the last available date in the database snapshot for subjects who were still on treatment at the time of an interim analysis.

The total duration of exposure to study drug will be summarized using descriptive statistics. Summaries will be provided by treatment and cohort for the Safety Analysis Set. The expected total duration of exposure is 1 day for subjects in Part A and 8 days for subjects in Part B.

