5.1.5.2 Incomplete Dates

If the onset date of the AE is incomplete and the AE stop date is not prior to the first dose date of any study drug, then the month and year (or year alone if month is not recorded) of onset determine whether an AE is treatment emergent. The event is considered treatment emergent if both of the following 2 criteria are met:

- The AE onset is the same as or after the month and year (or year) of the first dose date of study drug, and
- The AE onset date is the same as or before the month and year (or year) of the end of study.

An AE with completely missing onset and stop dates, or with the onset date missing and a stop date later than the first dose date of study drug, will be considered to be treatment emergent. In addition, an AE with the onset date missing and incomplete stop date with the same or later month and year (or year alone if month is not recorded) as the first dose date of any study drug will be considered treatment emergent.

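### SAP 5.4.2 compares partial medication dates strictly, so possible use during dosing that is dated only to the dosing month is generally tabulated as prior use alone

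*Combined protocol and SAP*

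**What the plan says.** SAP 5.4.2 (Concomitant Medications) has one bullet for partial dates, with two sentences.

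- **Partial start date.** The month and year, or the year alone, must be "before the study drug stop date, and with the stop date after the first dose date of study drug".
- **Partial stop date.** The sentence opens "If a partial stop date is entered, any medication with the month and year (if day is missing" and requires that month or year to fall after the first dose date.

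The same section treats other cases inclusively. Its full-date bullets accept a start on the first or last dose date, and accept use confined to either of those days. It also counts "Medications with completely missing start and stop dates, unless otherwise specified". A closing sentence excludes any medication that stopped before the first dose or started after the last dose.

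SAP 5.4.1 (Prior Medications) says that for a partial start date "the medication will be considered prior unless the month and year (if day is missing) or year (if day and month are missing") is later than the first dose. A start dated only to the dosing month is therefore prior.

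SAP 5.1.5.2 (Incomplete Dates) handles adverse events inclusively. Its lower bound for treatment emergence reads "The AE onset is the same as or after the month and year (or year) of the first dose date of study drug". Its upper bound, set by the end of study, is inclusive as well, and the rule applies when the event did not stop before the first dose.

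**The concern.** A month equal to the dosing month is neither before nor after it. On the literal text such a record fails both partial-date sentences of 5.4.2, while 5.4.1 places it among the prior medications. An adverse event carrying the same partial date is treatment-emergent.

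The rule also reverses the usual cautious logic. A medication with no dates at all is counted as concomitant, but one known to fall in the dosing month generally is not. What is at stake is the classification of possible use during dosing: it would be tabulated solely as use before dosing. If the authors meant *before* and *after* to include the same month, the text does not say so, and two programmers could code it differently.

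**Working it through.** The plan gives no figure to reproduce here, so the rules are applied as written.

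**Inputs.** The rules are those of SAP 5.4.1, 5.4.2 and 5.1.5.2. Dosing length comes from SAP 4.3.1: "The expected total duration of exposure is 1 day for subjects in Part A and 8 days for subjects in Part B".

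**Rules at month level.** Let F, L and E be the month and year of first dose, last dose and end of study.

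- Concomitant, start sentence: start month < L, and the stop date after first dose.
- Concomitant, stop sentence: partial stop month > F.
- Prior: start month not > F.
- Treatment-emergent adverse event: F ≤ onset month ≤ E.

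If F = L and the start month equals F, the start sentence fails whatever the stop date is, and the prior rule is met. The only route left is a partial stop date in a month after F.

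**Worked records, Part A, dosed 10 November (illustrative date).** A month alone means that the day is unknown.

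| Start | Stop | Prior | Concomitant as written | Concomitant with same-or comparisons |
|---|---|---|---|---|
| Nov | 20 Nov | yes | no | yes |
| Nov | Nov | yes | no | yes |
| Nov | 3 Dec | yes | no | yes |
| Nov | missing | yes | no | no |
| Nov | Dec | yes | yes | yes |
| Oct | Nov | yes | no | yes |

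An adverse event with onset dated only to November is treatment-emergent in this example. Three rows deserve comment.

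- **Rows 3 and 5:** a complete stop date of 3 December fails, while the vaguer December passes.
- **Row 4:** changing the comparisons alone does not help a record without a stop date.
- **Row 6:** a partial stop date in the dosing month is enough to fail, even when the start month is earlier. A complete start date before dosing does not rescue such a record, because the stop sentence still fails and the full-date bullet needs evidence that use continued past the first dose. In Part B, a complete start date after the first dose and up to the last dose qualifies through its own bullet.

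**How often F = L.**

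- Part A: one dosing day, so always, taking each dosing occasion separately.
- Part B: Day 8 is 7 days after Day 1. A month of m days has m − 7 start dates that keep both in the same month. Over a 365-day year this gives 365 − 12 × 7 = 281, and 281/365 = 77%.
- Part B, same calendar year (for year-only dates): 365 − 7 = 358, and 358/365 = 98%.

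**Part B dosing that crosses a month end** (84/365 = 23% of start dates), for example 27 November to 4 December:

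| Start | Stop | Prior | Concomitant as written |
|---|---|---|---|
| Nov | 30 Nov | yes | yes |
| Nov | Nov | yes | no |
| Dec | Dec | no | yes |

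Some records therefore escape when dosing spans two months, but not all.

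**The case against.** A reader might infer that the concomitant table will understate treatment of adverse events and hide breaches of the ban on concomitant drugs. The documents do not support that. SAP 5.4.2 separately excludes medications started after the last dose. With a single dose on Day 1, a fully dated drug started on Days 2 to 7 of Part A is outside the table whatever the partial-date bullet says, and the same holds after Day 8 in Part B. Breaches do not depend on this table either: SAP 4.2 summarises important protocol deviations and lists all deviations. For the same reason, the share of follow-up that falls in the dosing month is no measure of the problem, because that window extends beyond the last dose.

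Nor is every medication dated to the dosing month dropped, as the exceptions above show. Partial dates for on-study drugs should also be rare. Protocol 6.3 requires start and stop dates, subjects are confined through Day 4 (Part A) or Day 11 (Part B), and medications are checked at each scheduled visit. All medications remain in the by-subject listing.

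A further objection is that looser comparisons let in drugs that do not belong. Protocol 6.3.1 requires washout before Day 1, so a washed-out drug with a partial date in the dosing month could appear as on-study use. A drug dated only to the dosing month could be counted although its complete date would have excluded it.

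These points limit the consequence and shape the remedy. They do not remove the defect: the bullet states a rule, and for a date in the dosing month that rule generally gives an answer at odds with the rest of the section.

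**Conclusion.** The point holds as a minor error of rule wording. When first and last dose share a month, a partial start date in that month leads to prior-only classification unless a partial stop date falls in a later month, and a partial stop date in the dosing month fails the stop sentence. Possible use during dosing is then shown only as prior use.

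The documents do not say how many partial dates there will be; the number is likely small. The calendar shares say how often dosing meets the condition, not how many records are misclassified. No formal inference is planned and the listing is unaffected.

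The conclusion assumes that partial dates are compared literally at month or year level and, for the 77% and 98%, that each start date in a 365-day year is equally likely. It also takes each Part A dosing occasion on its own. If first and last dose are taken across the two periods of Cohort A7, or across Cohort A6 and the original cohort, they can fall in different months and the results for dosing across a month end apply.

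**What to change.** Replace the partial-date bullet in SAP 5.4.2 with the following rules.

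- **Partial start date:** count the medication when the month and year (or year) is the same as or before that of the last dose, and the medication is ongoing, has a missing stop date, or is not known to have stopped before the first dose.
- **Partial stop date:** count the medication when the month and year (or year) is the same as or after that of the first dose, and the start is not known to be after the last dose.
- **Overlap with 5.4.1:** state that such a medication may be counted as both prior and concomitant.
- **Last-dose exclusion:** state that it applies only when the available date parts show a start after the last dose.

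While editing, correct SAP 3.4.1, which points to Section 5.3 for the medication date rules; they are in 5.4.

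The cost is SAP wording and a small change to the derivation code before database lock. The downside is that a few medications with partial dates that were truly taken only before dosing (for example, washed out) or only after the last dose will also appear as concomitant. A table footnote saying that partial dates are resolved towards inclusion would make this plain.
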